4.3 Medication Formulations, Dosage and Administration

- 4.3.1 Everolimus is supplied by Novartis. Everolimus should be administered orally, once daily at the same time every day either consistently with food or consistently without food. Everolimus is available as dispersible tablets.
- 4.3.2 The dose of Everolimus is 4.5 mg/m²/day administered once a day. The initial calculated dose of Everolimus will be rounded either up or down to the nearest possible dose based upon available Dispersible Tablets (see section 4.4.3 below).
- 4.3.3 Everolimus will be supplied in the form of Dispersible Tablets (also referred to as 'tablets for oral suspension'): 2 mg, 3 mg and 5 mg.
- 4.3.4 Everolimus may be administered by either of the following two methods:
- 4.3.5 **Method 1, Using an oral syringe:** The required number of dispersible tablets (maximum of five 2 mg tablets, three 3 mg tablets, or two 5 mg tablets) should be placed into a 10 mL oral syringe. The plunger should be inserted and pushed inward to make contact with the dispersible tablet(s). A sufficient volume of water (approximately 5 mL) should be drawn up from a glass to cover the dispersible tablet(s). In addition, approximately 4 mL of air should be drawn up into the oral syringe. The filled oral syringe should be placed in a glass (tip up) and the contents left to disintegrate for 3 minutes. Prior to administration, the oral syringe should be inverted gently five times. While holding the oral syringe in an upright (tip up) position, excess air should be removed carefully. The full contents of the oral syringe should be immediately dispensed into the mouth of the patient, slowly and gently. The same volume of water and air should then be drawn up into the oral syringe, and the contents should be swirled to suspend any remaining particles. The contents should be administered as previously described to ensure the entire dose is administered.

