4.5 Recommended Dose of Everolimus

The recommended starting dose is 4.5 mg/m²/dose, once daily. Continue treatment for up to 2 years, until disease progression or unacceptable toxicity occurs. After 2 years of therapy, patients will complete the study protocol, but may continue therapy using commercially available drug based upon the clinical judgment of their treating physician and the child's parents or guardians.

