4.5.1 Dose modification and dose delay

4.5.1.1 Therapeutic drug monitoring: Therapeutic drug monitoring of Everolimus blood concentrations is required for patients enrolled on study and taking Everolimus. Testing is to be performed by Quest Diagnostics using a validated bioanalytical LC/MS method (test code 18883X). Trough concentrations should be assessed 2 weeks (+/- 4 days) after the initial dose, after any change in dose or formulation, after an initiation or change in co-administration of CYP3A4 inducers or inhibitors, or after any change in hepatic status.

4.5.1.2 Dosing modifications:

Titrate the dose to attain trough concentrations of 5 to 15 ng/mL.

- For trough concentrations less than 5 ng/mL, increase the daily dose by 2 mg and repeat trough concentration in 2 weeks (+/- 4 days).
- For trough concentrations greater than 15 ng/mL, reduce the daily dose by 2 mg and repeat trough concentration in 2 weeks (+/- 4 days).
- The lowest possible dose level of Everolimus is 2 mg daily.
- If dose reduction is required for patients receiving the lowest available strength, administer every other day.

- For patients who do not tolerate the protocol-specified dosing schedule, dose adjustments are permitted in order to allow the patient to continue the study treatment. Dose levels are as follows: Level -2 = 3 mg/m²/dose, Level -1 = 3.8 mg/m²/dose, Level 0 = 4.5 mg/m²/dose, Level +1 = 5.2 mg/m²/dose and Level +2 = 6 mg/m²/dose. If dose adjustments need to be made for toxicity, patients' doses of Everolimus should not be targeted to achieve a trough level of 5 – 15 ng/mL.

Table 4-1**Dosing guidelines for Everolimus-related non-hematologic toxicities**

Toxicity	Action
Non-Infectious Pneumonitis	Please refer to Table 4-3.
Reactivation of HBV or HCV flare	Please refer to Table 4-5.
AST or ALT elevation	Maintain current dose level
Grade 1 (> ULN - 3.0 x ULN)	
Grade 2 (> 3.0 - 5.0 x ULN)	
AST or ALT elevation Grade 3 (> 5.0 - 20.0 ULN)*	Interrupt Everolimus administration until resolution to ≤ grade 1 (or ≤ grade 2 if baseline values were within the range of grade 2). If resolution occurs ≤ 7 days, Everolimus should be re-started at the dose level prior to interruption. If resolution takes > 7 days, or if event recurs within 28 days, hold Everolimus until recovery to ≤ grade 1 or baseline grade / value and reintroduce Everolimus at one dose level lower, if available.

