- For patients with elevated Everolimus trough levels (>15 ng/ml), decrease dose by 25% and repeat trough concentration in 2 weeks.
- Co-administration with strong inducers or inhibitors of CYP3A4 is strongly discouraged and should be discussed with the study chair. If a patient requires co-administration of strong CYP3A4 inducers (i.e., phenytoin, carbamazepine, rifampin, rifabutin, phenobarbital, St. John's wort), an increase in the dose of Everolimus may be necessary. Enzyme induction usually occurs within 2 weeks; therefore Everolimus dose should be increased by one increment 7 days after the start of the inducer therapy. If no safety concerns are seen within the next 7 days, the dose can be increased again one additional increment up to a maximum of twice the daily dose used prior to initiation of the strong CYP3A4 inducer.
- This dose adjustment of Everolimus is intended to achieve similar AUC to the range observed without inducers. However, there are no clinical data with this dose adjustment in patients receiving strong CYP3A4 inducers. If the strong inducer is discontinued the Everolimus dose should be returned to the dose used prior to initiation of the strong CYP3A4/PgP inducer. Please refer to Table 4-7 listing relevant inducers and inhibitors of CYP3A and Table 4-8 for a list of relevant substrates, inducers, and inhibitors of PgP.

Table 4-7
isoenzyme CYP3A

Clinically relevant drug interactions: inducers, and inhibitors of

Inducers:

carbamazepine, glucocorticoids, modafinil, oxcarbazepine, phenobarbital, phenytoin, pioglitazone, rifabutin, rifampin, St. John's wort, troglitazone, efavirenz, nevirapine, topiramate, avasimibe, bosentan, etravirine, naftcillin, ritonavir, talviraline (not available in US market), tipranavir, amprenavir, aprepitant, armodafinil (R-modafinil), dexamethasone, nevirapine, prednisone, pleconaril (not available in US market), rufinamide

Inhibitors:

Strong inhibitors:

clarithromycin, conivaptan, indinavir, itraconazole, ketoconazole, lopinavir, mibefradil, nefazodone, nelfinavir, ritonavir, saquinavir, telithromycin, troleandomycin, voriconazole, tipranavir, elvitegravir, Posaconazole ([Krishna et al 2009](#))

Moderate inhibitors:

aprepitant, atazanavir, casopitant, cimetidine, ciprofloxacin, darunavir, diltiazem, erythromycin, fluconazole, grapefruit juice (citrus paradisi fruit juice), imatinib, tofisopam, verapamil, amprenavir, fosamprenavir, dronedarone

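### At 3 mg daily, the 2 mg cut for a trough above 15 ng/mL gives 1 mg, a dose the plan rules out, and the neighbouring rules do not agree on what to do instead

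*Combined protocol and SAP*

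**What the plan says.** Dosing starts from body surface area: "The recommended starting dose is 4.5 mg/m²/dose, once daily" (section 4.5). Under section 4.3.2 the initial calculated dose "will be rounded either up or down to the nearest possible dose" that the dispersible tablets allow, and section 4.3.3 lists strengths of 2, 3 and 5 mg.

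Titration then aims at a trough of 5 to 15 ng/mL. Four statements bear on a level that is too high:

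- Section 4.5.1.2, the step: "For trough concentrations greater than 15 ng/mL, reduce the daily dose by 2 mg and repeat trough concentration in 2 weeks".
- Section 4.5.1.2, the floor: "The lowest possible dose level of Everolimus is 2 mg daily".
- Section 4.5.1.2, the fallback: "If dose reduction is required for patients receiving the lowest available strength, administer every other day".
- Section 4.6.2, among the CYP3A4 and P-glycoprotein bullets: "For patients with elevated Everolimus trough levels (>15 ng/ml), decrease dose by 25% and repeat trough concentration in 2 weeks".

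Tables 4-1 and 4-2 repeat the 2 mg floor for toxicity that recurs after a dose reduction, and add that everolimus has to be discontinued below it. Section 5.2.4 says only that an out-of-range level leads to an adjustment towards the target; it names no step.

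**The concern.** A flat 2 mg step is a very different proportion of a small dose than of a large one, and the smallest tablet is itself 2 mg. The step therefore has to be checked at the bottom of the dose range. At 3 mg, following the instruction as written leads to a dose that the plan excludes.

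This rule is there for safety. Section 1.4 gives the avoidance of excessive exposure as the reason for measuring troughs, and section 10.6 requires the study to be run as the protocol describes. If the instruction cannot be followed literally, two sites could handle the same child differently and each could point to some text in support. In a trial of 18 patients, handling that depends on the site is worth removing when the cost is small. If a site took the discontinuation wording from the toxicity tables, that child could also count towards the permanent-discontinuation limit in section 7.6.

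**Working it through.** **Inputs.** Starting dose 4.5 mg/m²/day (4.5); strengths 2, 3 and 5 mg (4.3.3); nearest-dose rounding (4.3.2); step of minus 2 mg above 15 ng/mL and floor of 2 mg daily (4.5.1.2); step of minus 25% above 15 ng/mL (4.6.2). Tablets are assumed not to be split.

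**The plan's floor.** The sums of 2, 3 and 5 mg tablets are 2, 3, 4, 5, 6 mg and every whole milligram above. 1 mg is not among them. The stated floor of 2 mg daily is therefore also the smallest daily dose that the tablets can make.

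**Both steps applied to each low dose.** The percentage cut under 4.5.1.2 is 2 / dose.

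| Current daily dose | Minus 2 mg (4.5.1.2) | Cut | Dispensable, at or above floor? | Minus 25% (4.6.2) | Nearest makeable |
|---|---|---|---|---|---|
| 2 mg | 0 mg | 100% | No; every-other-day line applies | 1.5 mg | 2 mg |
| 3 mg | 1 mg | 67% | No; no line written for it | 2.25 mg | 2 mg |
| 4 mg | 2 mg | 50% | Yes | 3 mg | 3 mg |
| 5 mg | 3 mg | 40% | Yes | 3.75 mg | 4 mg |
| 6 mg | 4 mg | 33% | Yes | 4.5 mg | 4 or 5 mg (tie) |
| 7 mg | 5 mg | 29% | Yes | 5.25 mg | 5 mg |
| 8 mg | 6 mg | 25% | Yes | 6 mg | 6 mg |

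Only 3 mg gives a result that is below the floor, cannot be made, and has no fallback written for it. The last column applies nearest-dose rounding to a later adjustment. That is an assumption, since 4.3.2 states the rule for the initial dose.

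**Who takes 3 mg.** The rounding limits are 2.5 / 4.5 = 0.556 m² and 3.5 / 4.5 = 0.778 m². A child in that band starts on 3 mg; below 0.556 m² the start is 2 mg. A child who started higher can also arrive there, since 5 − 2 = 3 mg, and is affected if the repeat trough is still above 15 ng/mL.

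**The neighbouring text at 3 mg.**

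- *The floor.* Read as a cap, it stops the step at 2 mg: (3 − 2) / 3 = a 33% cut. Read as a separate statement, it contradicts the ordered 1 mg.
- *The every-other-day line.* It is written for a child on the lowest strength, which is 2 mg, so it does not literally cover 3 mg. It also conflicts with the floor, because 2 mg every other day averages 1 mg a day.
- *Tables 4-1 and 4-2.* They call for discontinuation below 2 mg daily, but in rows about recurrent toxicity, not troughs.
- *Section 4.6.2.* For the same trigger it gives 3 × 0.75 = 2.25 mg. This also cannot be made exactly, and it differs from the 1 mg ordered in 4.5.1.2.

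**The case against.** The strongest answer is that the three statements in 4.5.1.2 are meant to be read together. The step comes first, then the floor, then the fallback. On that reading the floor caps the step, a child on 3 mg goes to 2 mg, and if the level is still high the every-other-day line then applies. This is a sensible reading, and a careful site might well adopt it. But the text does not say that the floor caps the step. The reading also leaves unexplained how alternate-day dosing at 2 mg fits a floor expressed per day, and why 4.6.2 has a different step for the same trough.

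It can also be said that the 25% rule is confined to patients on interacting drugs, because of where it sits. That may be the intention, but its wording carries no such limit. Likewise, the discontinuation wording belongs to toxicity, and 4.5.1.2 takes patients whose dose was adjusted for toxicity out of trough targeting. That makes discontinuation the weakest of the readings, though not one that the text expressly excludes for troughs.

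Two stronger readings are tempting and should not be drawn:

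- A reader might infer that the rule breaks down in the smallest children. It does not. Those below 0.556 m² start on 2 mg and have the every-other-day line. The gap follows a single dose, not size.
- A reader might infer that the flat step also fails at the top of the range, because sections 4.3.5 and 4.3.6 allow a "maximum of five 2 mg tablets, three 3 mg tablets, or two 5 mg tablets". Those are tablet counts for one syringe or one glass (10, 9 and 10 mg respectively). Neither section states a daily ceiling.

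It also stands that doses differ between children by design, that a repeat trough follows any change, and that inconsistent handling by sites is a possibility, not something the documents show.

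**Conclusion.** The point holds in a narrow form. For a child on 3 mg daily with a trough above 15 ng/mL, section 4.5.1.2 as written orders 1 mg. The plan's own floor excludes that dose and the supplied tablets cannot make it. The surrounding text supports more than one action and does not choose between them.

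The ordered cut is 67%. Capping at the floor would make it 33%, and the 25% rule gives 2.25 mg before any rounding. These figures assume whole tablets; the starting band of about 0.56 to 0.78 m² also assumes nearest-dose rounding. The documents give neither a distribution of body surface area nor an expected frequency of troughs above 15 ng/mL, so the number of children affected cannot be estimated and could be zero.

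The two-stage design in section 9.2 and the response analysis in section 9.3 do not depend on this. It is an inconsistency in a safety-directed instruction that is cheap to remove and should be corrected. It does not show that the dosing scheme as a whole is unworkable.

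**What to change.** Reconcile sections 4.3.2 and 4.3.3, 4.5.1.2, the 2 mg floor rows of Tables 4-1 and 4-2, and 4.6.2, so that:

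- one rule applies to a trough above 15 ng/mL, with the scope of the 25% step in 4.6.2 stated (all patients, or only those on interacting drugs);
- every dispensable daily dose, including 3 mg, has one stated next-lower step, most simply in a lookup table;
- the relation between the 2 mg daily floor and the every-other-day line is explicit;
- it is clear whether the discontinuation wording in the toxicity tables has any bearing on trough-driven reductions.

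The choice of doses and of the governing rule rests with the sponsor. The cost is one dosing table in 4.5.1.2 and matching cross-references, submitted as an amendment under section 10.7. No visit, blood sample or patient is added, and the sample size does not change.

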AST or ALT elevation Grade 4 (> 20 x ULN)*	Interrupt Everolimus administration until resolution to ≤ grade 1 (or ≤ grade 2 if baseline values were within the range of grade 2). If resolution occurs ≤ 7 days, Everolimus should be re-started at one dose level lower. If resolution takes > 7 days, discontinue Everolimus.
Recurrence of Grade 4 AST or ALT elevation after dose reduction or toxicity requiring Everolimus interruption for > 28 days	Discontinue Everolimus.
Intolerable grade 2 mucositis, or grade 3 AE, except hyperglycemia or hypertriglyceridemia or hypercholesterolemia	Interrupt Everolimus administration until resolution to ≤ grade 1 or baseline grade / value. If resolution occurs within ≤ 7 days, Everolimus should be re-started at the dose level prior to interruption. If resolution takes > 7 days, or if event recurs within 28 days, hold Everolimus until recovery to ≤ grade 1 or baseline grade / value and reintroduce Everolimus at one dose level lower, if available. Patients will be withdrawn from the study if they fail to recover to ≤ grade 1 or baseline grade / value within 28 days.
Any other grade 4	Hold Everolimus until recovery to grade ≤ 1 or baseline value Reintroduce Everolimus at one dose level lower, if available.
Grade 3 or 4 clinical liver failure (asterixis or encephalopathy/coma)	Discontinue Everolimus
Recurrence of intolerable grade 2 mucositis or grade 3 event after dose reduction	Reduce dose to the next lower dose level, if available. The lowest possible dose level of Everolimus is 2 mg daily. Below this level, Everolimus must be discontinued.
Recurrence of grade 4 after dose reduction	Discontinue Everolimus
Any non-hematologic toxicity requiring Everolimus interruption for > 28 days	Discontinue Everolimus

* Should HCV flare be confirmed, the guidelines for flare must take precedence (Table 4-4).

Table 4-2**Dosing guidelines for Everolimus-related hematologic toxicities**

Toxicity	Action
Grade 2 thrombocytopenia (platelets <75, \geq 50x109/L)	Interrupt Everolimus until resolution to grade \leq 1 If resolution occurs \leq 7 days, reintroduce Everolimus at the dose level prior to interruption. If resolution occurs $>$ 7 days, or event occurs within 28 days, reintroduce Everolimus at one dose level lower, if available.

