Grade 3 thrombocytopenia (platelets <50, \geq 25 x109/L)	Interrupt Everolimus until resolution to grade \leq 1 If resolution occurs \leq 7 days, reintroduce Everolimus at the dose level prior to interruption. If resolution occurs $>$ 7 days, or event occurs within 28 days, reintroduce Everolimus at one dose level lower, if available.
Grade 4 thrombocytopenia (platelets < 25 x109/L)	Interrupt Everolimus until recovery to grade \leq 1. Then reintroduce Everolimus at one dose level lower, if available.
Grade 3 neutropenia or anemia (neutrophil <1, \geq 0.5 x109/L)	Interrupt Everolimus until resolution to grade \leq 2 or baseline value If AE resolution occurs \leq 7 days, reintroduce Everolimus at the same dose level. If AE resolution occurs $>$ 7 days, or event occurs within 28 days, reintroduce Everolimus at one dose level lower, if available.
Grade 4 neutropenia or anemia	Interrupt Everolimus until recovery to grade \leq 2 or baseline value. Reintroduce Everolimus at one dose level lower, if available.*
Grade 3 febrile neutropenia	Interrupt Everolimus until resolution to grade \leq 1 (or baseline value) and no fever. Reintroduce Everolimus at one dose level lower, if available.*
Grade 4 febrile neutropenia	Discontinue treatment
Recurrence of grade 3 toxicity after dose reduction	Reduce dose to the next lower dose level, if available. The lowest possible dose level of Everolimus is 2 mg daily. Below this level, Everolimus must be discontinued.
*Recurrence of grade 4 toxicity (including febrile neutropenia) after dose reduction	Discontinue Everolimus
*Any hematologic toxicity requiring Everolimus interruption for $>$ 28 days	Discontinue Everolimus

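### The mg/m² dose levels are spaced more finely than whole tablets allow, so in some small children a required step to the next lower level leaves the daily dose unchanged, and after trough titration the step is undefined

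*Combined protocol and SAP*

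**What the plan says.** For patients who do not tolerate the schedule, Section 4.5.1.2 lists five levels: "Level -2 = 3 mg/m²/dose, Level -1 = 3.8 mg/m²/dose", then "Level 0 = 4.5 mg/m²/dose, Level +1 = 5.2 mg/m²/dose and Level +2 = 6 mg/m²/dose". Section 4.3.3 supplies dispersible tablets of 2, 3 and 5 mg only. Section 4.3.2 says that the initial calculated dose "will be rounded either up or down to the nearest possible dose based upon available Dispersible Tablets"; no section states how a reduced dose is rounded.

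Tables 4-1 and 4-2 use the level scale after toxicity. For grade 4 AST or ALT elevation that resolves within 7 days, "Everolimus should be re-started at one dose level lower". After grade 4 thrombocytopenia, "Then reintroduce Everolimus at one dose level lower, if available". Other rows are similar.

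Two further rules bear on the same doses:

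- **At the floor.** Section 4.5.1.2 puts the lowest level at 2 mg daily and tells sites to give the drug on alternate days if a patient on the lowest strength needs a reduction. The rows of Tables 4-1 and 4-2 on recurrence after a reduction require discontinuation below 2 mg daily.
- **Trough titration.** Section 4.5.1.2 moves the daily dose up or down by a flat 2 mg when the trough is outside 5-15 ng/mL.

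**The concern.** Dose levels are set per m², tablets come in whole milligrams, and trough titration moves in flat 2 mg steps. Nothing in the protocol converts one scale to another. Eligibility starts at age 2 (Section 3.1.1), and in small children a gap of 0.7 mg/m² is worth less than one tablet step. A site could follow Table 4-1 or 4-2 to the letter and hand out the same tablets as before. A child whose dose has been titrated may not be on any listed level, so there is no defined level to step down from.

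The first stake is the response to serious toxicity in children. The second is how later rules are applied. Both tables prescribe a different action when toxicity recurs after a dose reduction, and after grade 4 that action is discontinuation. If the reduction existed only on paper, it is unclear whether those rows apply. Permanent discontinuations count toward the stopping rule in Section 7.6 (4 of the first 10 patients or 6 of the first 16).

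**Working it through.** The plan gives no mg equivalents for the levels, so there is no figure of its own to reproduce. The check is deterministic.

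**Inputs.** Levels 3.0, 3.8, 4.5, 5.2 and 6.0 mg/m² and the 2 mg floor (Section 4.5.1.2); tablets of 2, 3 and 5 mg (Section 4.3.3); nearest-dose rounding (Section 4.3.2).

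**Assumptions.** Whole tablets; ties rounded up; rounding extended to reductions; BSA range and even spread as stated below, because the documents give no BSA data.

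**1. Deliverable doses.** Sums of 2, 3 and 5 mg give 2, 3, 4, 5, 6 ... mg: every whole milligram from 2 mg up. The smallest step is 1 mg. A gap of 0.7 mg/m² is worth 1 mg only at 1/0.7 = 1.43 m², and a gap of 0.8 mg/m² at 1/0.8 = 1.25 m².

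**2. Where Levels 0 and -1 dispense the same dose.** Under nearest rounding, a level L dispenses d mg when (d - 0.5)/L ≤ BSA < (d + 0.5)/L. Both levels dispense d when (d - 0.5)/3.8 ≤ BSA < (d + 0.5)/4.5.

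| Shared dose d | Lower bound (m²) | Upper bound (m²) | Width |
|---|---|---|---|
| 3 mg | 2.5/3.8 = 0.658 | 3.5/4.5 = 0.778 | 0.120 |
| 4 mg | 3.5/3.8 = 0.921 | 4.5/4.5 = 1.000 | 0.079 |
| 5 mg | 4.5/3.8 = 1.184 | 5.5/4.5 = 1.222 | 0.038 |
| 6 mg | 5.5/3.8 = 1.447 | 6.5/4.5 = 1.444 | none |

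For example, at 0.70 m² Level 0 is 3.15 mg and Level -1 is 2.66 mg; both dispense 3 mg. At 0.85 m² they are 3.83 and 3.23 mg, dispensed as 4 and 3 mg, so there the step works.

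Below 2.5/4.5 = 0.556 m² Levels 0, -1 and -2 all come to 2 mg. The floor rules govern that case (step 5).

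**3. Levels -1 and -2.** By the same method both dispense 3 mg at 2.5/3.0 = 0.833 to 3.5/3.8 = 0.921 m² (width 0.088), and 4 mg at 3.5/3.0 = 1.167 to 4.5/3.8 = 1.184 m² (width 0.018).

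**4. Size under an even BSA spread, leaving out shared doses of 2 mg.**

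- Level 0 to -1, 0.5-1.0 m²: (0.120 + 0.079)/0.5 = 40%.
- Level 0 to -1, 0.5-1.8 m²: (0.120 + 0.079 + 0.038)/1.3 = 18%.
- At least one of the two downward steps empty: (0.199 + 0.088)/0.5 = 57% of 0.5-1.0 m², and (0.237 + 0.088 + 0.018)/1.3 = 26% of 0.5-1.8 m².

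*Sensitivity to rounding.* Always rounding down moves the Level 0/-1 bands to 3/3.8-4/4.5 = 0.789-0.889 m² (3 mg), 4/3.8-5/4.5 = 1.053-1.111 m² (4 mg) and 5/3.8-6/4.5 = 1.316-1.333 m² (5 mg). The shares become 0.100/0.5 = 20% and (0.100 + 0.058 + 0.017)/1.3 = 13%. The empty steps are fewer but remain.

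**5. The 2 mg floor.** For a child on 2 mg daily who needs a reduction, Section 4.5.1.2 gives alternate-day dosing and the recurrence rows of Tables 4-1 and 4-2 give discontinuation. Neither place limits its rule so as to leave room for the other.

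**6. Trough titration.** At 0.6 m² the starting dose is 4.5 × 0.6 = 2.7 mg, dispensed as 3 mg. One upward step gives 5 mg, or 5/0.6 = 8.3 mg/m². The top listed level is 6 × 0.6 = 3.6 mg, dispensed as 4 mg, so 5 mg matches no level. Ignoring rounding, one upward step from Level 0 passes Level +2 whenever 4.5 + 2/BSA > 6, that is, below 2/1.5 = 1.33 m².

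**The case against.** Several objections have force.

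- **Rounding is stated only for the initial dose.** Correct; extending it to reductions is an inference. But no other rule is given for reduced doses, and rounding down leaves empty steps too.
- **Most rows say a lower level applies only if one is available.** A level that tablets cannot deliver can fairly be read as unavailable. The protocol does not say so, nor what follows: the same dose, a further step down, or stopping. The grade 4 AST/ALT row carries no such qualifier.
- **Not every grade 3 or 4 event calls for a reduction.** Many grade 3 events that resolve within 7 days restart at the prior level, and some grade 4 events mean discontinuation. The point concerns only the rows that do require a lower level.
- **The smallest children are covered.** A reader might infer that a child of 0.50-0.55 m² stays on an unchanged 2 mg daily, because three levels round to 2 mg. The text does not support that: either floor rule changes treatment. The defect there is the conflict between the rules. Counting these cases as empty steps would raise the Level 0 to -1 share of 0.5-1.0 m² from 40% to 51%.
- **Exposure data would be intact.** A reader might infer a distorted tolerability analysis. Section 4.1 requires all prescribed and dispensed doses to be recorded, Section 4.4.3 reconciles tablet counts and the diary records mg, so an unchanged dose would be visible. Section 9.3 plans exact binomial estimates for safety and no analysis of dose reductions.
- **8.3 mg/m² breaks no stated ceiling.** Titration is trough-driven and subject to tolerability, and the level list is not presented as a maximum. What stands is that the next lower level is undefined for such a child.

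**Conclusion.** The point holds as an operational gap in the dose-reduction rules; no stated figure in the plan is wrong. Under nearest rounding, Levels 0 and -1 dispense the same 3, 4 or 5 mg in three BSA bands between 0.658 and 1.222 m², and a mandated reduction there can be empty. Above about 1.22 m² this does not happen. The value of 1.43 m², where 0.7 mg/m² equals 1 mg, is a theoretical bound and not the reach of the problem. Separately, the rules at 2 mg contradict each other, and titrated children can sit off the level scale.

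The band limits follow from the protocol's levels and tablets once the rounding rule is extended to reductions. The shares (40% of 0.5-1.0 m², 18% of 0.5-1.8 m²) also rest on an assumed even BSA spread and say nothing about how many enrolled children would be affected. It would go too far to conclude that reductions generally fail in small children: between the bands the step lowers the dose by 1 mg.

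**What to change.** Reconcile five items by amendment: the level list in Section 4.5.1.2, the rounding rule in Section 4.3.2 (including whether it covers reductions), the tablet strengths in Section 4.3.3, the flat 2 mg titration steps, and the conflicting rules at the 2 mg floor in Section 4.5.1.2 and Tables 4-1 and 4-2. Afterwards each required reduction should correspond to a different dispensed dose, or the protocol should state for which BSA or current dose no lower level is available and what then applies. It should also say which level, if any, a titrated child is on, and whether a step that leaves the dose unchanged counts as a dose reduction in the recurrence rows. The doses and rules are for the clinical team to decide.

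The cost is small: a dosing table by BSA band and matching wording in the two toxicity tables. Sample size, endpoints, planned analyses and data collection do not change.
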